4.7. Interim Analysis	32
4.8. Changes to Protocol-planned Analyses.....	32

5.	Sample Size Determination	33
6.	Supporting Documentation	34
6.1.	Appendix 1: List of Abbreviations.....	35
6.2.	Appendix 2: Supporting Study Information.....	36
6.2.1.	Disposition of Subjects.....	36
6.2.2.	Demographics.....	36
6.2.3.	Baseline and Disease Characteristics	37
6.2.4.	Treatment Compliance	38
6.2.5.	Protocol Deviations	38
6.2.6.	Medical History and Concurrent Illnesses	38
6.2.7.	Prior/Concomitant Medications and Procedures	39
6.3.	Appendix 3: Data Handling Conventions	40
6.3.1.	Analysis Visit Windows.....	40
6.3.2.	Missing Date Imputation	40
6.3.3.	Multiple Imputation and Rubin's Rule.....	41
6.4.	Appendix 4: Schedule of Assessments.....	43
6.5.	Appendix 5: Efficacy Assessments	46
6.5.1.	PGA	46
6.5.2.	CCI	47
6.5.3.	mPASI	47
6.5.4.	CCI	49
6.5.5.	CCI	49
6.5.6.	CCI	49
7.	References	51

Version History

SAP Version	Date	Change	Rationale
1.0	01Dec2023	Not applicable	Original version
1.1	20Dec2023	Minor	
Remove coding of light therapy (section 6.2.3).
 
Specify 2 additional decimal places to present SD (section 4.1.1).

1.2	02Feb2024	Major	
Add description of estimand strategy when there are few subjects with an IMP discontinuation due to pandemic restriction (section 4.1.5).
 
Specify both baseline PGA strata and baseline value of the endpoint as covariate in logistic and ANCOVA model (section 4.1.5).
 
Update SAS sample code (section 6.3.3).

1.3	29Feb2024	Minor	
Update wording of estimand strategy (section 4.1.5) and add the updates to section 4.8.
 
Change summary of lab results out of reference range from “events reported up to week 6” to “events reported up to end of study” (section 4.5.3.1) and add the updates to section 4.8.

1.4	13Mar2024	Minor	
Update wording of estimand strategy (section 4.1.5).
 
Record the change of adding baseline score value to logistic regression in section 4.8.

2.0	29Mar2024	Minor	Wording updates.

1. Introduction

This trial is conducted to assess efficacy and safety of LEO 90100 when used on the body for the treatment of stable plaque psoriasis in adult Chinese subjects, compared to Daivobet® ointment, which is approved in China for the treatment of stable plaque psoriasis on the body.

The Statistical Analysis Plan (SAP) details the statistical methodology to be used in analysing study data and outlines the statistical programming specifications for the Tables, Figures and Listings (TFLs). It describes the variables and populations, anticipated data transformations and derivations and other details of the analyses not provided in the Clinical Study Protocol (CSP). In case of discrepancies between CSP and SAP ([Section 4.8](#)), the SAP supersedes the CSP.

The SAP will be finalized prior to Database Lock (DBL). The analyses described in this SAP are based upon the following study documents:

- Clinical Study Protocol, Version 3.0 (November 9th, 2022)
- electronic Case Report Form (eCRF), Version 3.0 (November 2nd, 2023)

1.1. Objectives, Endpoints, and Estimands

1.1.1. Primary objective, related endpoints and primary estimands

Table 1-1 Primary Objective, Related Endpoints and Primary Estimands

Primary Objective	Endpoints	Primary Estimands
To evaluate the efficacy of LEO 90100 compared with Daivobet® ointment on severity and extent of stable plaque psoriasis.	
Primary endpoint
 
 Having PGA score of 0 (clear) or 1 (almost clear) at Day 29, with at least a 2-point reduction from baseline. 
Key secondary endpoint
 
 Having a decrease in mPASI of at least 75% (mPASI-75) from baseline to Day 29. 
Secondary endpoint
 
 Having a decrease in mPASI of at least 90% (mPASI-90) from baseline to Day 29. 	
 Composite strategy will be used to address permanent discontinuation of IMP not due to pandemic restrictions.¹ Hypothetical strategy will be used to address permanent discontinuation of IMP due to pandemic restrictions.²

Abbreviations: AE=adverse events; CCI [REDACTED]; COVID-19=coronavirus disease 2019; IMP=investigational medicinal product; mPASI=modified Psoriasis Area and Severity Index; mPASI-75=a decrease in mPASI of at least 75%; mPASI-90=a decrease in mPASI of at least 90%; PGA=Physician's Global Assessment of disease severity.

¹ **Permanent discontinuation of IMP not due to pandemic restrictions:** This event occurs when a subject permanently discontinues IMP for reasons not related to pandemic restrictions. This event can occur either at the subject's own initiative or at the investigator's or sponsor's discretion. The timing of the event will be the date following the date of last IMP administration. Permanent discontinuation of IMP due to sickness with COVID-19 (an AE) will be interpreted as permanent discontinuation of IMP not due to pandemic restrictions.

² **Permanent discontinuation of IMP due to pandemic restrictions:** This event occurs when a subject permanently discontinues IMP for reasons related to pandemic restrictions. Examples of permanent discontinuation of IMP due to pandemic restrictions are quarantines (i.e., subjects who have or have a suspicion they have COVID-19 and are not allowed on to site for visits due to quarantine measures imposed), travel limitations, subject being unable or unwilling

to travel to site due to personal pandemic-related reasons, site closures, reduced availability of site staff and interruptions to the supply chain of IMP. The timing of the event will be the date following the date of last IMP administration. Permanent discontinuation of IMP due to sickness with COVID-19 (an AE) will not be interpreted as permanent discontinuation of IMP due to pandemic restrictions, unless caused by quarantine measures.

1.1.2. Secondary and **cci** objectives and endpoints

Table 1-2 Secondary and **cci** Objectives and Endpoints

Objectives	Endpoints
Secondary To evaluate the safety of LEO 90100 compared with Daivobet® ointment treating stable plaque psoriasis.	Secondary endpoint • Number of TEAEs from baseline to Day 43 per subject.
cci	cci
cci	cci
cci	cci
	cci

Abbreviations: **cci** ; **cci**
cci ; TEAEs=treatment-emergent adverse events.

1.2. Study Design

This phase 3, randomised, prospective, investigator-blinded, active-controlled, parallel group, multicentre trial will evaluate the efficacy and safety of 4 weeks treatment with LEO 90100 compared with Daivobet® ointment in native Chinese subjects (aged ≥ 18 years) with at least mild stable plaque psoriasis.

600 trial subjects are planned to be randomised in a 1:1 ratio to either LEO 90100 or Daivobet® ointment treatment. Randomisation will be stratified by Physician's Global Assessment of disease severity (PGA) at baseline (mild [PGA=2], moderate [PGA=3] or severe [PGA=4]).

For each subject, the trial will last 6 weeks to 10 weeks, including:

- A washout/screening period up to 4 weeks (at least 1 visit);

- A treatment period up to 4 weeks (3 visits);
- A safety follow-up period of 2 weeks (1 visit for all subjects 2 weeks after the last IMP administration).

The subjects will provide written consent according to national laws and regulations before any trial-related activities are carried out.

Washout/Screening Period

For subjects who have been receiving prohibited medications prior to screening, the screening period may be extended up to 4 weeks to ensure they complete the required washout period before they start receiving the IMP. On completion of the washout period, confirmation of the subject's ongoing eligibility for the trial will be made at Day 1 (baseline). However, if no washout is needed the subject will enter Day 1 (baseline) directly.

Treatment Period

[figure not shown]
The treatment period will last for up to 4 weeks and includes 3 visits: Visit 2 (Day 1), Visit 3 (Week 2) and Visit 4 (Week 4). The start of IMP treatment will be at Day 1 and this visit will be considered as baseline. The first application of the IMP will be made at site under supervision and instruction of an unblinded member of the trial staff (not the investigator, as this is an investigator-blinded trial) at the Day 1 visit. The subjects also have the option to apply the first IMP at home after the instruction has been given at the site.

Follow-up Period

The follow-up visit (Visit 5) will be performed at Week 6, which is 2 weeks after the last visit in the treatment period.

The trial design is illustrated in [Figure 1-1](#) and visit schedule is provided in [Appendix 4](#).

Figure 1-1 Trial Design

Abbreviations: N=number of subjects; No.=number; w=weeks.

2. Statistical Hypotheses

The primary endpoint will first be evaluated for non-inferiority (at threshold $T=\text{CCI}$) and subsequently superiority 2-sided hypotheses will be tested for LEO90100 versus Daivobet[®] ointment.

The key secondary and one secondary endpoints will be evaluated for superiority 2-sided for LEO 90100 versus Daivobet[®] ointment.

Treatment effect will be defined as odds ratio (OR), and binary endpoints will be tested as follows for:

- Non-inferiority: $H_0: \text{OR} \leq T$ against $H_a: \text{OR} > T$.
- Superiority: $H_0: \text{OR} \leq 1$ against $H_a: \text{OR} > 1$.

2.1. Multiplicity Adjustment

The primary endpoint, the key secondary endpoint and the other secondary endpoint are included in a closing testing procedure with hierarchical tests will be used to control the overall type I error at nominal 2-sided 5% level. The hypothesis relating to a specific endpoint cannot be rejected unless all hypotheses earlier in the hierarchy are also rejected.

The confirmatory conclusions from the confirmatory testing strategy will be based on the results from the primary analyses of the primary estimands. The primary endpoint will first be evaluated for non-inferiority and if the 95% confidence interval (CI) for the treatment effect (on the OR scale) not only lies entirely above the non-inferiority threshold ($T=\text{CCI}$) but also above 1 then there is evidence of superiority in terms of statistical significance at the 2-sided 5% level.

[figure not shown]
In this case, it is acceptable to calculate the p-value associated with a test of superiority and evaluate whether this is sufficiently small (two-sided p-value <0.05) to reject the hypothesis of no difference. In the switch from non-inferiority to superiority there is no multiplicity argument that affects the interpretation because, in statistical terms, it corresponds to a simple closed test procedure.

The complete superiority testing scheme is described below and illustrated in [Figure 2-1](#). If non-inferiority is confirmed the following 3 hypotheses will be tested sequentially:

- No difference in the proportion of subjects with at least a 2-point PGA reduction from baseline having PGA score of 0 (clear) or 1 (almost clear) at Day 29 between LEO 90100 and Daivobet® ointment treatment.
- No difference in the proportion of subjects having mPASI-75 at Day 29 between LEO 90100 and Daivobet® ointment treatment.
- No difference in the proportion of subjects having mPASI-90 at Day 29 between LEO 90100 and Daivobet® ointment treatment.

The trial is considered a success if non-inferiority is confirmed for the primary endpoint. The non-inferiority margin of 10% on the OR scale, is equivalent to a non-inferiority threshold of $T = \underline{CCI}$.

Figure 2–1 **Graphical Display of Closed Testing Procedure for Primary, Key Secondary and Secondary Endpoints**

Abbreviations: mPASI=modified Psoriasis Area and Severity Index; PGA=Physician's Global Assessment.

3. Analysis Sets

For purposes of analyses, the following analysis sets are defined:

Table 3–1 **Subject Analysis Sets**

Subject Analysis Set	Description
All screened set	All screened subjects.
All randomised subjects	All randomised subjects.
Full analysis set (FAS)	All randomised subjects.
	
Subjects will be included in the analyses according to randomised treatment allocation. Exclusions from the FAS can be considered in special cases, as described in Section 5.2.1 (Full Analysis Set) of ICH E9 guidelines^[1].
 
If a subject is excluded from the FAS, a justification per ICH E9 guidelines^[1] will be given.

Safety analysis set	All subjects who are exposed to the IMP. Subjects will be analysed according to the treatment they actually received.

Abbreviations: FAS=full analysis set; IMP=investigational medicinal product.

The all screened set will be used for summary of subject disposition.

The all randomised subjects will be used for summary of demographic and baseline characteristics.

The full analysis set (FAS) will be used for the analysis of efficacy data and the safety analysis set will be used for the analysis of safety data.

The decisions regarding inclusion/exclusion of subjects or subject data from the analysis sets will be taken by during a blinded data review meeting and will be documented with reasons for exclusions, before unblinding of the trial.

All subjects screened in the trial will be accounted for in the clinical trial report (i.e., subjects for whom informed consent has been obtained and who have been registered in the trial).

4. Statistical Analyses

4.1.2. Baseline Definition

Baseline measurements will be defined as the latest available observation at or prior to the date of randomisation.

Scheduled assessments taken on the same day as randomisation will be assumed as prior to randomisation. If the unscheduled assessment is recorded on the same day as randomisation, the unscheduled assessment will be assumed to be post-randomisation, unless there is clear evidence showing that the assessment is prior to randomisation.

4.1.3. Study Day

Study Day will be calculated from the randomisation date or the first IMP administration date, whichever occurs first. Study day of the randomisation or the first IMP administration date will be Day 1.

- If the date of interest is on or after the randomisation date, then:

Study Day = [date of assessment/interest – minimum (randomisation date, first IMP administration date)] + 1

- If the date of interest is prior to the randomisation date, then:

Study Day = [date of assessment/interest – minimum (randomisation date, first IMP administration date)]

When the date of assessment/interest is partial or missing, study day will not be calculated, unless otherwise specified.

4.1.4. Randomisation Strata

The randomisation will be stratified by PGA at baseline:

- Mild (PGA=2)
- Moderate (PGA=3)
- Severe (PGA=4)

In statistical analyses where strata are included, the stratification factors will be included as collected in the Interactive Web Response System (IWRS) at randomisation. If a subject is stratified incorrectly, “actual stratum” will be used rather than “randomised stratum”.

4.1.5. Estimand Strategy

4.1.5.1. General Considerations

The analysis of endpoints related to efficacy will be based on the FAS.

An intercurrent event (IE) refers to a post-randomisation event that affects either the interpretation or the existence of the measurements of an endpoint. For the purposes of this trial, the following 2 IEs are defined:

- **Permanent discontinuation of IMP not due to pandemic restrictions:** This IE occurs when a subject permanently discontinues IMP for reasons not related to pandemic restrictions. This event can occur either at the subject's own initiative or at the investigator or sponsor's discretion. The timing of the event will be the date following the date of last IMP administration. Permanent discontinuation of IMP due to sickness with COVID-19 (an AE) will be interpreted as permanent discontinuation of IMP not due to pandemic restrictions.

- **Permanent discontinuation of IMP due to pandemic restrictions:** This IE occurs when a subject permanently discontinues IMP for reasons related to pandemic restrictions. Examples of permanent discontinuation of IMP due to pandemic restrictions are quarantines (i.e., subjects who have or have a suspicion they have COVID-19 and are not allowed on to site for visits due to quarantine measures imposed), travel limitations, subject being unable or unwilling to travel to site due to personal pandemic-related reasons, site closures, reduced availability of site staff and interruptions to the supply chain of IMP. The timing of the event will be the date following the date of last IMP administration. Permanent discontinuation of IMP due to sickness with COVID-19 (an AE) will not be interpreted as permanent discontinuation of IMP due to pandemic restrictions, unless caused by quarantine measures.

Note, there is a distinction between permanent discontinuation of IMP (an IE) and withdrawal from trial and/or lost to follow-up. Withdrawal from trial and lost to follow-up, which are not IEs, will be addressed when specifying methods and/or assumptions for handling missing data. If the withdrawal from trial is related to the pandemic restrictions, missing data will be handled as missing data related to the pandemic restrictions.

The death of a subject has not been described above as an IE since occurrences of this event is considered unlikely in the setting of this trial. Should it happen that a subject dies, then analyses will handle this using the same strategy as described below for addressing permanent discontinuation of IMP due to pandemic restrictions.

The following strategies will be implemented for handling the IEs (ICH E9 [R1] guidelines^[2]):

- The ‘hypothetical’ strategy attempts to quantify the effect of treatment in the hypothetical situation where IEs do not occur.
- The ‘treatment policy’ strategy attempts to quantify the effect of the decision to treat subjects with the randomised treatment, thus ignoring the occurrence of IEs.
- The ‘composite’ strategy accounts for the occurrence of IEs, through the definition of a suitable composite endpoint, whose components include the aforementioned IEs, as well as the endpoint of interest.

Depending on the strategy selected, the occurrence of an IE may lead to the exclusion of data observed after the occurrence of the event, be ignored, be accounted for in the definition of a

composite endpoint or restrict the relevant observation window to the time prior to the occurrence of the IE.

Prior to DBL, IE of permanent discontinuation of IMP due to pandemic restriction and missing data due to pandemic restriction were not observed among all subjects. Therefore, all estimand analyses will be based on the strategy of having only IE and missing data not due to pandemic restriction.

For each efficacy endpoint associated with a trial objective, a primary estimand will be pre-specified. For the binary endpoints a secondary estimand will be used to further aid in the interpretation of the results (see Section 4.1.5.2 and Section 4.1.5.3).

The following primary and secondary estimands will be defined:

- The primary estimand for binary endpoints will use a ‘composite’ strategy to handle IEs for subjects who have permanently discontinued IMP independently of pandemic restrictions prior to the Week 4 visit (Visit 4). Subjects will be imputed as non-responders, reflecting an assumption that permanent discontinuation of IMP independent of pandemic restrictions indicates failure of the randomised treatment to achieve response. A ‘hypothetical’ strategy, in the form of a multiple imputation method (see Appendix 6.3.2.1), will be used to address permanent discontinuation of IMP due to pandemic restrictions. For subjects who have permanently discontinued IMP due to pandemic restrictions prior to Week 4 (Visit 4) data collected after permanent discontinuation of IMP will be replaced by model-based predictions.
- Differently from the primary estimand for the binary endpoints, the secondary estimand for binary endpoints will use “treatment policy” strategy to handle IEs for subjects who have permanently discontinued treatment independently of pandemic restrictions prior to the Week 4 visit (Visit 4). Data will be used as observed.
- The primary estimand for continuous endpoints will use the same strategies applied for the secondary estimand for binary variables.

The occurrence of IEs will be listed and summarised by treatment group. Table 4-1 presents an overview of how observed and missing data will be handled according to the IEs for the primary analysis for estimands.

Parexel International
Statistical Analysis Plan

Table 4-1 Handling of Observed and Missing Data According to the IEs for the Primary Analysis for Estimands

IE	Data observed or missing	Estimands for binary endpoints		Estimand for continuous endpoints
		Primary	Secondary	
Permanent discontinuation of IMP not due to pandemic restrictions	Observed	Composite: N/A, value of the endpoint is determined by the IE (non-response)	Treatment policy: Used as observed	Treatment policy: Used as observed
	Missing	N/A, value of the endpoint is determined by the IE (non-response)	MI (MAR within treatment arms)	MI (MAR within treatment arms)
Permanent discontinuation of IMP due to pandemic restrictions	Observed	Hypothetical: Treated as missing, MI (MAR within treatment arms)	Hypothetical: Treated as missing, MI (MAR within treatment arms)	Hypothetical: Treated as missing, MI (MAR within treatment arms)
	Missing	MI (MAR within treatment arms)	MI (MAR within treatment arms)	MI (MAR within treatment arms)
No IE	Observed	Used as observed	Used as observed	Used as observed
	Missing not due to pandemic restrictions	NRI	MI (MAR within treatment arms)	MI (MAR within treatment arms)
	Missing due to pandemic restrictions	MI (MAR within treatment arms)	MI (MAR within treatment arms)	MI (MAR within treatment arms)

Abbreviations: IE=intercurrent event; IMP=investigational medicinal product; MAR=missing at random; MI=multiple imputation; N/A=not applicable; NRI=non-responder imputation.

Parexel International Statistical Analysis Plan

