1. Under missing at random (MAR) assumption within treatment arm, binary response at Week 4 (or Week 2) will be imputed for subjects who have permanently discontinued IMP due to pandemic restrictions prior to Week 4 (or Week 2) and for subjects who have not permanently discontinued IMP prior to Week 4 (or Week 2) and whose score at Week 4 (or Week 2) is missing due to pandemic restrictions. Fully conditional specification (FCS) method will be implemented to impute missing binary responses by implementing logistic or regression methods (number of imputed datasets = 1000; seed = 2)[3]. FCS logistic regression will be implemented for the binary PGA and ~~CCI~~ endpoints. FCS linear regression will be utilised to impute the mPASI score. Binary mPASI-75 and mPASI-90 will be derived from the imputed score. Response at Week 4 (or Week 2) will be imputed using the stratification PGA, the value baseline score value (not for PGA as it coincides with the randomisation strata) and response at the Week 2 visit (not applicable when imputing data for Week 2) as covariates.
2. Non-responder imputation will be applied for subjects who have not permanently discontinued IMP prior to Week 4 (or Week 2) and whose binary response at Week 4 (or Week 2) is missing for reasons other than pandemic restrictions.
3. A logistic regression model will be implemented to estimate each subject's probability of permanent discontinuation of IMP not due to pandemic restrictions up until Week 4 (Day 29) among subjects who permanently discontinued IMP due to pandemic restrictions. Stratification PGA, sex and age will be utilised as covariates. Using the subject predicted probability (p_i) of discontinuation, the following steps will be followed to derive the treatment adherence variable:
 - a. For each imputed dataset, a value from the exponential distribution with rate p_i will be drawn and multiplied with 29 to obtain days (starting seed = 3)
 - b. Person-days already spent in the trial will be added to the drawn number
 - c. Derive the treatment adherence variable with the following categorisation:
 - Days < 15 : subject discontinued before Week 2
 - $15 \leq \text{Days} < 29$: subject discontinued after Week 2 and before Week 4
 - $\text{Days} \geq 29$: the subject did not discontinue.

d. For subjects predicted to be discontinued before Week 2 or Week 4, non-responder imputation will be applied to the visits after the predicted discontinuation.

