Table 4–2 Hypothetical Strategy for Addressing Permanent Discontinuation of IMP Due to Pandemic Restrictions and Handling of Missing Data in the Primary Analysis of the Primary Estimand

Step no.	Description	Subjects in scope for imputation	Purpose
1	Impute binary (0/1) response at Week 4 under MAR assumptions within treatment arm	Subjects who have permanently discontinued IMP due to pandemic restrictions prior to Week 4.	Hypothetical strategy
		Subjects who have not permanently discontinued IMP prior to Week 4 and whose score at Week 4 is missing due to pandemic restrictions.	Handling of missing data
2	Impute binary (0/1) response at Week 4 based on NRI	Subjects who have not permanently discontinued IMP prior to Week 4 and whose score at Week 4 is missing for reasons other than pandemic restrictions.	Handling of missing data
3	Impute treatment adherence status at Week 4 within treatment arm	Subjects who have permanently discontinued IMP due to pandemic restrictions prior to Week 4.	Hypothetical strategy

Abbreviations: IMP=investigational medicinal product; MAR=missing at random; NRI=non-responder imputation.

Sensitivity Analysis of the Primary Estimand

For the sensitivity analysis, which is rather conservative against the LEO 90100 group, observed data at Week 4 will be used in the Daivobet® ointment group for the subjects who permanently discontinued IMP not due to pandemic restrictions. In addition, missing data for subjects in the Daivobet® ointment group will be imputed, as described in Point 1 of hypothetical strategy summarised in [Table 4–2](#).

Primary Analysis of the Secondary Estimand

For the primary analysis of the secondary estimand, under MAR assumption within treatment arm, binary response at Week 4 will be imputed for subjects who have permanently discontinued IMP due to pandemic restrictions prior to Week 4 and for subjects who have not permanently

discontinued IMP prior to Week 4 and whose score at Week 4 is missing due to pandemic restrictions. FCS method will be applied, as described for the primary analysis of the primary estimand.

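### The SAP sends a death before Week 4 to the pandemic imputation branch, which the same section says is not used; the primary binary analysis needs one rule

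*SAP*

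**What the plan says.** **The death rule.** SAP 4.1.5.1 explains why death is not on the list of intercurrent events (IEs): "The death of a subject has not been described above as an IE since occurrences of this event is considered unlikely". It then says that if a subject "dies, then analyses will handle this using the same strategy as described below for addressing permanent discontinuation of IMP due to pandemic restrictions". Protocol 9.3.5.1 has the same rule.

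**What that strategy is.** For the primary estimand of the binary endpoints (PGA success, mPASI-75, mPASI-90), SAP 4.1.5.2 and Tables 4-1 and 4-2 define it as multiple imputation (MI) under missing at random (MAR) within arm. A third step follows: "Impute treatment adherence status at Week 4 within treatment arm". SAP 4.1.5.2 adds: "For subjects predicted to be discontinued before Week 2 or Week 4, non-responder imputation will be applied to the visits after the predicted discontinuation".

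**Everything not due to the pandemic.** For permanent discontinuation unrelated to the pandemic the rule is composite: "Subjects will be imputed as non-responders, reflecting an assumption that permanent discontinuation of IMP independent of pandemic restrictions indicates failure". For a subject with no IE, the Table 4-1 row "Missing not due to pandemic restrictions" gives non-responder imputation (NRI) in the primary estimand.

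**The pandemic branch set aside.** SAP 4.1.5.1 also reports that no pandemic discontinuation and no pandemic-related missing data had been seen before database lock. It concludes that "all estimand analyses will be based on the strategy of having only IE and missing data not due to pandemic restriction".

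**The concern.** Followed as written, the death sentence lets a subject who dies before Week 4 be counted as a treatment responder in some or all of the imputed datasets. The documents give no reason for choosing this strategy. That death is unlikely explains only why it is not listed as an IE.

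The result is odd next to its neighbours. SAP 4.1.5.1 treats stopping treatment because of COVID-19 illness as a non-pandemic discontinuation, hence a non-response, unless quarantine caused it. Dying of the same illness would go to MI.

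The later statement says that only the non-pandemic strategy will be used. The death sentence then points to a branch that is not run. Neither sentence refers to the other, Tables 4-1 and 4-2 have no entry for death, and none of the three changes in SAP 4.8 concerns it. At stake is whether the confirmatory analysis has one defined result for a death.

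**Working it through.** **1. Route one death before Week 4 through the text (primary analysis, primary binary estimand).**

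| Rule followed | Place | Week 4 result |
|---|---|---|
| Death sentence | SAP 4.1.5.1, Protocol 9.3.5.1 | MI: response or non-response, by draw |
| Non-pandemic strategy, no IE, value missing | SAP Table 4-1, no-IE rows | NRI: non-response |
| Non-pandemic strategy, death read as a discontinuation | SAP Table 4-1, first rows | Composite: non-response |

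The first row cannot be applied together with either of the others. It is also incompletely specified: step 3 in SAP 4.1.5.2 models adherence among pandemic discontinuers, of whom the SAP reports none.

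**2. Reproduce the plan's figures.** Inputs from Protocol 9.5 and SAP 5: 54.6% (LEO 90100), 43.0% (Daivobet ointment), 300 per arm.
- OR = (0.546/0.454)/(0.430/0.570) = 1.594, against 1.59 stated.
- Exact enumeration with the Fisher-type 95% limit gives superiority 0.8016 (stated 0.799), non-inferiority 0.9224 (stated 0.9198) and P(OR > 1) 0.9975 (stated 0.9975). The non-inferiority threshold is redacted; 0.90 and 1/1.1 were each assumed and give the same value.
- The plan's power simulation draws from fixed response rates and does not model deaths, so these figures do not depend on the death rule.

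**3. Expected response credited to one death under MI.** Step 3 draws days = 29 × Exp(rate p) + d, where d is days already in the trial, and keeps the subject on treatment if days ≥ 29. So P(stay) = exp(−p(29 − d)/29). The documents give no discontinuation rate; p = 0.03 to 0.10 and d = 1 to 28 are assumed.
- Lowest (p = 0.10, d = 1): exp(−0.10 × 28/29) = 0.908. Highest (p = 0.03, d = 28): 0.999. If step 3 is not applied to deaths: 1.
- LEO 90100: 0.546 × 0.908 = 0.496, up to 0.546.
- Daivobet: 0.430 × 0.908 = 0.390, up to 0.430.
- Under non-response: 0 in either arm.

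**4. Shift in the crude OR (MI minus non-response).**
- One LEO 90100 death: the other 299 subjects give 299 × 0.546 = 163.25 responders. Non-response: (163.25/136.75)/(129/171) = 1.5825. MI: 1.5931 to 1.5942. Shift +0.0106 to +0.0117.
- One Daivobet death: the other 299 give 299 × 0.430 = 128.57 responders. Non-response: (163.8/136.2)/(128.57/171.43) = 1.6036. MI: 1.5951 to 1.5942. Shift −0.0085 to −0.0094.
- Three deaths in one arm: +0.032 to +0.035 (LEO 90100) or −0.026 to −0.028 (Daivobet).

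These are expected values at marginal planning rates. The actual imputation also conditions on baseline PGA and Week 2 response. The documents give no planning rates for mPASI-75 or mPASI-90.

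**The case against.** The strongest reply is that an express rule for one event does not contradict a general rule for others. The death rule stands in both documents and may be a deliberate exception. The set-aside statement rests on the absence of pandemic events, so the death rule could be dormant rather than overruled. It is true that an unexplained exception is not in itself an inconsistency. But if the exception survives, a death can be imputed as a response through a step that does not cover deaths. If it does not survive, the sentence contradicts the operative rule. Either way the text needs correcting.

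Four stronger readings might be inferred, and the documents do not support them.

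- *That death is plainly a non-pandemic IE.* The definition, "This IE occurs when a subject permanently discontinues IMP for reasons not related to pandemic restrictions", is broad, and the end-of-treatment form in Protocol 7.1 lists death apart from pandemic restrictions. But SAP 4.1.5.1 says death is not described as an IE, and it describes the discontinuation as arising at the initiative or discretion of the subject, investigator or sponsor. The NRI row is the more natural route. The result is non-response either way.
- *That the choice would have to be made with treatment known.* Protocol 6.4.1 requires an approved SAP update before unblinding, and SAP 3 provides for a blinded data review. There is a route to settle it blind.
- *That the rule favours LEO 90100.* The shift favours whichever arm has the death.
- *That SAP 4.8 omitted a change to the death rule.* The rule is unchanged from the protocol, so there was nothing to list. The SAP version history (version 1.2) does record the added text on few pandemic discontinuations.

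**Conclusion.** The point holds as a minor correction: the death rule is wrong as written for the primary analysis of the primary binary estimand. It can credit a death with a response, and it conflicts with the statement that only the non-pandemic strategy is used.

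The size is about 0.01 on the OR per death, assuming 300 per arm and the planning rates. The lower end of each range also rests on the assumed 3–10% discontinuation and on applying step 3 to deaths. If the pandemic branch is in fact not run, a death is already a non-response and the difference is nil. It is also nil if nobody died; the documents call death unlikely and do not say whether any occurred.

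The conflict does not carry over to the secondary binary or continuous estimands, where every missing-data row of Table 4-1 is already MI.

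**What to change.** Before unblinding, replace the death sentence in SAP 4.1.5.1 with:

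> In the primary analysis of the primary estimand for binary endpoints, a subject who dies before the Week 4 assessment is a non-responder at Week 4 and at any visit after death. Responses observed before death are kept for earlier visits. The sensitivity analysis of the primary estimand, the secondary binary estimand and the continuous estimands follow Sections 4.1.5.2 and 4.1.5.3 and Table 4-1 unchanged.

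The limits matter. The sensitivity analysis imputes missing Daivobet data on purpose, to be conservative against LEO 90100; forcing Daivobet deaths to non-response there would weaken it. An observed Week 2 response should not be overwritten by a later death.

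Add to SAP 4.8, because Protocol 9 asks for a reason for each change:

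> Death before Week 4 is non-response in the primary analysis of the primary binary estimand, instead of the pandemic strategy in Protocol 9.3.5.1. The pandemic branch is not used, and a death should not be imputed as a response; this agrees with the handling of other non-pandemic discontinuation and missing data.

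The cost is one replaced sentence and one log entry, with no new data and no change to design or power. SAP 1 gives the SAP precedence over the protocol, so the protocol text need not be amended.
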